sided alpha level of 0.05 and 90% power, the required sample size was estimated to be 27 participants per treatment arm. Anticipating a dropout rate of approximately 40%, the total planned enrollment was therefore set at 90 participants. Due to delays associated with the COVID-19 pandemic and lack of financial resources to continue the study, recruitment was terminated before reaching the intended enrollment target. Following the decision to stop recruitment, a revised power calculation—based on the originally specified primary endpoint and the same effect size assumptions as the initial power analysis—indicated that 22 participants per treatment arm would provide approximately 85% power, corresponding to a total of 44 completers. As of December 2025, the observed dropout rate was substantially lower than anticipated (13%), resulting in 59 enrolled participants, of whom 51 completed the primary endpoint assessment. The number of completers therefore exceeded the minimum sample size required according to the revised power calculation. Of these, 28 completed fMRI scans, however only those with complete behavioural data and adequate quality imaging data for analyses will be retained for analyses. Imaging data will be quality controlled using fMRIPrep.

TRIAL POPULATION

Recruitment

Recruitment began September 2023 and ended September 2025. Last patient's last visit in the main trial i.e., the 12-week outcome assessment was on 22nd December 2025. Last patient's last visit concluding the entire study i.e., the 26-week follow-up will be end of March 2026. Participants were recruited in part from outpatient clinics, but predominantly from society via advertisement.

Eligibility

Treatment seeking individuals aged 20-70, weighing 60-95kg, diagnosed with AUD and alcohol dependence according to DSM-V and ICD-10, respectively, who had at least 5 heavy drinking days within the past 28 days of screening, and no co-occurring substance use disorders (except nicotine) and no concomitant pharmacotherapy for AUD.

OUTCOMES

OUTCOME CATEGORY	SOURCE	TIME POINTS	PRIMARY COMPARISON (BETWEEN-GROUP DIFFERENCE)
Primary			
1. Percentage of Heavy Drinking Days (PHDD)	TLFB/28 days	BL, W4, W8, W12	W12, adjusted for BL
Secondary			
2. Alcohol consumption:			
• % drinking days	TLFB/28 days	BL, W4, W8, W12	W12, adjusted for BL
• Drinks per day	TLFB/28 days	BL, W4, W8, W12	W12, adjusted for BL
• Drinks per drinking day	TLFB/28 days	BL, W4, W8, W12	W12, adjusted for BL

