For continuous outcomes, analyses will use a baseline-adjusted linear mixed model for repeated measures including all observed timepoints for the given outcome. The primary estimand is the between-group difference in mean change from baseline at Week 12 (unless otherwise specified). Model assumptions will be assessed using standard diagnostic methods. If substantial deviations from model assumptions are observed, appropriate transformations of the outcome or alternative modeling approaches will be considered as sensitivity analyses.

Categorical outcomes assessed at a single time point will be analyzed using chi-square or Fisher’s exact tests as appropriate. Repeated categorical outcomes will be analyzed using GEE or generalized linear mixed models.

Missing data

Missing data will be handled using full information maximum likelihood (FIML), which uses all available observed data to estimate model parameters under the missing at random (MAR) assumption. While the

MAR assumption may not be valid we will also consider sensitivity analyses by setting missing observations to extreme but realistic values to bound realistic effect size. See below.

Sensitivity analysis

Because the MAR assumption cannot be formally tested, pre-planned sensitivity analyses will be conducted under missing not at random (MNAR) assumptions. Specifically, missingness is assumed to potentially depend on factors related the unobserved Week 12 outcome values. The following conservative scenarios will be evaluated:

- Complete-case analysis: Analyses will be restricted to participants with observed values at both baseline and the Week 12 endpoint. In the case of neuroimaging data, only complete cases will be analysed.
- Single imputation (conservative MNAR scenario): For participants with missing Week 12 data, the continuous Week 12 outcome will be imputed as a 50% reduction from the individual's baseline value (i.e., Week 12 = $0.5 \times$ baseline), and the primary analysis model will be re-estimated.

Per protocol analysis

A per-protocol (PP) analysis will be conducted including only participants who did not violate key protocol requirements through Week 12. The PP analysis is intended to estimate the effect of the intervention under full protocol adherence and will be interpreted cautiously due to the potential for selection bias.

Pre-specified mechanistic/exploratory analyses

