Analyses will examine associations between selected secondary endpoints and the primary endpoint. These analyses are intended to assess relationships between outcomes and to inform hypotheses regarding potential mechanisms of action. Associations will be evaluated using correlation analyses and/or regression models as appropriate, without adjustment for multiplicity.

- Week 1 neural differentiation between alcohol and neutral cues, quantified using latent variable scores from a mean-centering Partial Least Squares (PLS) analysis of whole-brain blood oxygenation level-dependent (BOLD) responses, and associations with subsequent changes in alcohol consumption and brain-derived neurotrophic factor (BDNF) levels. Resting-state functional connectivity at Week 1 (striatum to salience-network, and within control-network connectivity) and their associations with changes in alcohol consumption and changes in BDNF levels.
- Acute subjective effects during the dosing session and their associations with changes in alcohol consumption and changes in BDNF levels.

Significance level

The primary endpoint will be tested using a one-sided significance level of 0.05 with corresponding 95% confidence intervals, reflecting an a priori directional hypothesis that psilocybin will reduce heavy drinking days compared with placebo. The direction of the primary hypothesis and the use of one-sided testing were prespecified prior to database lock and unblinding and were informed by consistent evidence from prior

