clinical studies. Effects in the opposite direction, if observed, will be fully reported and interpreted descriptively. All secondary and exploratory analyses will be conducted using two-sided significance tests. For Partial Least Squares fMRI analyses, latent variable significance will be assessed via permutation testing (1,000 permutations, $p < 0.05$), with voxel reliability determined by bootstrap ratios $\geq |2.5|$ (200 bootstrap iterations). The PLS analysis will include group (psilocybin vs placebo) as a between-subjects factor, testing for group \times condition (alcohol vs neutral) interactions in whole-brain BOLD responses. Additionally, a separate single-group PLS analysis (collapsing across psilocybin and placebo groups) will be performed to derive individual latent variable scores reflecting each participant's neural differentiation between alcohol and neutral cues. These individual LV scores will be correlated with changes in alcohol consumption from baseline to Week 12. No multiplicity adjustments will be performed, and no additional covariate adjustments will be applied except for the baseline value of the endpoint in question.

Statistical software

All statistical analysis will be performed with R. fMRI data will be preprocessed using fMRIPrep v25.1.0 (<https://fmriprep.org/en/stable/>) and denoised using Nilearn in Python. Partial Least Squares analyses are performed using the Rotman-Baycrest PLS Toolbox in MATLAB. Resting-state functional connectivity analyses will be performed using custom code in MATLAB.

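### The SAP names full maximum likelihood as the estimation method and gives no small-sample correction; if fitted that way, the primary test would be slightly too lenient

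*SAP*

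**What the plan says.** The SAP, under Efficacy analyses, sets the model for continuous outcomes: a "baseline-adjusted linear mixed model for repeated measures including all observed timepoints". The target is given in the same place: "The primary estimand is the between-group difference in mean change from baseline at Week 12", unless otherwise specified.

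Under Missing data it then says: "Missing data will be handled using full information maximum likelihood (FIML), which uses all available observed data to estimate model parameters", on the assumption that data are missing at random (MAR).

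Under Significance level: "The primary endpoint will be tested using a one-sided significance level of 0.05 with corresponding 95% confidence intervals". Secondary and exploratory tests are two-sided, and "no additional covariate adjustments will be applied except for the baseline value of the endpoint in question".

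The numbers available are under Sample size: "resulting in 59 enrolled participants, of whom 51 completed the primary endpoint assessment".

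The SAP does not mention REML, a degrees-of-freedom method, a reference distribution for the tests or a covariance structure. Statistical software names R and no fitting option for the mixed models.

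**The concern.** Full information maximum likelihood is maximum likelihood. An analyst who takes the Missing data sentence at its word would fit the mixed model by ML. ML estimates the residual covariance as though the fixed effects were known, so the variance is biased downwards. The bias vanishes in a large trial but can be seen with about 50 participants. If the test statistic is then referred to the normal distribution, a second small error adds to the first in the same direction.

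The standard errors, and hence the confidence intervals, would be a little too small and the true error rates a little above the stated ones. This would apply to the primary outcome and to the other continuous outcomes analysed under the same rule, which are tested without multiplicity adjustment. REML uses the same observations under the same MAR assumption and largely removes the bias, so ML offers no advantage here.

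**Working it through.** The SAP gives no standard error or test size to reproduce. The benchmark is its nominal level: 0.05 one-sided for the primary test and a 95% confidence interval.

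**Inputs from the SAP**
- Enrolled 59, assessed at Week 12 51, so 59 − 51 = 8 missing (Sample size).
- Post-baseline visits for the primary outcome: Weeks 4, 8 and 12 (Outcomes table).
- Mean parameters at Week 12: intercept, baseline and arm, so p = 3 (baseline is the only covariate allowed, under Significance level).

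**Assumptions not in the SAP:** normal errors, an unstructured covariance, and either a normal or a t reference.

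**Step 1. Closed form for a baseline-adjusted comparison at Week 12, n = 51**

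ML divides the residual sum of squares by n, and REML divides it by n − p. Hence

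SE(ML) / SE(REML) = √((n − p)/n) = √(48/51) = 0.970,

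so the ML standard error is 3.0% too small.

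Under the null, the estimate divided by the REML standard error follows t on n − p = 48 df. The true size of an ML test with critical value c is therefore P(t48 > 0.970 × c) in one tail, and twice that for a two-sided test.

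| Test | Reference | c | 0.970 × c | True size |
|---|---|---|---|---|
| One-sided 5% | normal | 1.645 | 1.596 | 5.86% |
| One-sided 5% | t, 48 df | 1.677 | 1.627 | 5.51% |
| Two-sided 5% | normal | 1.960 | 1.901 | 6.33% |
| Two-sided 5% | t, 48 df | 2.011 | 1.951 | 5.70% |

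If n = 59 is used instead, the ratio is √(56/59) = 0.974. The one-sided sizes become 5.73% (normal) and 5.44% (t).

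**Step 2. Simulation of the repeated-measures model**

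The closed form treats the 51 completers as the whole data set, whereas the planned model also uses earlier visits from participants without Week 12. A null simulation took this into account: 59 participants, 8 missing Week 12, visits at Weeks 4, 8 and 12, and an unstructured covariance. Further assumptions were a within-person correlation of 0.5 or 0.7, a common or visit-specific baseline slope, and dropout unrelated to outcome. There were 6,000 runs for each of the four settings, and Monte Carlo error on the size is about 0.2 percentage points.

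| Fit and reference | One-sided size | 95% interval coverage |
|---|---|---|
| ML, normal | 5.4 to 5.7% | 93.8 to 94.3% |
| ML, t on 48 df | 5.0 to 5.3% | 94.5 to 94.9% |
| REML, t on 48 df | 4.6 to 4.9% | 95.0 to 95.3% |

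The ratio of ML to REML standard error was 0.971 to 0.975, which agrees with the closed form.

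**Step 3. Combined range for the one-sided primary test**

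Taking the lowest simulated and the highest closed-form value gives 5.4 to 5.9% with a normal reference and 5.0 to 5.5% with a t reference. The excess over nominal is therefore about 0 to 0.9 percentage points.

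**The case against.** The strongest reply is that the sentence stands under Missing data and explains how incomplete records contribute, as opposed to deletion or imputation. The model itself is set under Efficacy analyses, where no estimator is named. On that reading FIML is a loose label for likelihood-based use of all observed data, and a REML fit would be consistent with it. This stands as a possible reading. It does not make the wording adequate, because the sentence says that FIML is how the parameters are estimated, and nothing else in the SAP points an analyst to REML.

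The second reply is that the larger figures need a normal reference, which the SAP does not specify. This also stands. With a t reference, the simulated one-sided excess is between nil and 0.3 points, close to Monte Carlo error.

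The third is that the closed form overstates the effect, because the planned model uses more than the 51 completers and because normal errors are assumed for what is a bounded percentage. The simulation deals with the first part and gives somewhat smaller figures. The second part remains an assumption of both calculations.

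A reader might infer that the planned intervals are definitely too narrow and that the primary error rate definitely exceeds 5%. The SAP does not support this. It follows only if the model is fitted by plain ML without correction, and its size depends on a reference distribution that is left open. Nor should the two-sided 6.3% be read as the error rate of the primary test, which is one-sided.

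**Conclusion.** The point holds in conditional form and is of low importance. Followed literally, the SAP leads to an ML fit with no small-sample correction. The Week 12 standard error would then be about 3% too small, and the one-sided primary test would run at about 5.4 to 5.9% (normal reference) or 5.0 to 5.5% (t reference). The two-sided secondary tests would run at about 6.3% or 5.7% by the closed form at n = 51.

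The choice between ML and REML, the reference distribution and the covariance structure are all assumptions of this review, as are normal errors and, in the simulation, dropout unrelated to outcome. An effect of this size would matter only for a result close to the significance boundary.

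**What to change.** Replace the FIML wording with a sentence to this effect: mixed models are fitted by REML using all available observations (valid under MAR), with Kenward-Roger or Satterthwaite degrees of freedom for tests and confidence intervals. Make the change as a dated amendment before the analyses are run.

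The cost is one sentence, and the method is standard in R. No observations are lost and the MAR assumption is unchanged. The downside is slightly wider intervals. In the closed form at n = 51, the 95% interval widens by 1/0.970 = 1.03, about 3%, relative to ML with a t reference. Relative to ML with a normal reference it widens by 2.011/(1.960 × 0.970) = 1.06, about 6%.

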• Total alcohol (g/day)	TLFB/28 days	BL, W4, W8, W12	W12, adjusted for BL
• % abstinent days	TLFB/28 days	BL, W4, W8, W12	W12, adjusted for BL

•	WHO risk levels	TLFB/28 days	BL, W4, W8, W12	W12, adjusted for BL
•	PEth	Blood	BL, W4, W8, W12	W12, adjusted for BL
•	GGT	Blood	BL, W12	W12, adjusted for BL
•	ALAT	Blood	BL, W12	W12, adjusted for BL
•	MCV	Blood	BL, W12	W12, adjusted for BL
3.	Brain imaging and neuroplasticity			
•	Alcohol cue-related BOLD response and in-scan craving ratings (alcohol > neutral)	fMRI	W1	W1 (post-treatment only)
•	Resting-state functional connectivity between striatum and salience -network regions	fMRI	W1	W1 (post-treatment only)
•	BDNF	Blood	BL, dosing, W1, W12	W1, adjusted for BL
4.	Psychometrics			
•	SETS	Questionnaire	BL	BL
•	PACS	Questionnaire	BL, W1, W4, W8, W12	W12, adjusted for BL
•	AUDIT	Questionnaire	BL, W12	W12, adjusted for BL
•	DUDIT	Questionnaire	BL, W12	W12, adjusted for BL
•	AASE	Questionnaire	BL, W1, W4, W8, W12	W12, adjusted for BL
•	MDI	Questionnaire	BL, W1, W4, W8, W12	W12, adjusted for BL
•	MAAS	Questionnaire	BL, W1, W4, W8, W12	W12, adjusted for BL
•	AAQ	Questionnaire	BL, W1, W4, W8, W12	W12, adjusted for BL
•	SF-36	Questionnaire	BL, W4, W12	W12, adjusted for BL
•	NEO-PI	Questionnaire	BL, W4, W12	W12, adjusted for BL
•	FTND	Questionnaire	BL, W4, W8, W12	W12, adjusted for BL
•	PEQ	Questionnaire	W4, W12	W12
5.	Acute effects			
•	SDI	VAS (0-10)	Dosing (0–360 min)	Association with W12 alcohol outcomes, adjusted for baseline
•	MEQ30 / 11D-ASC / EBI / EDI / AWE	Questionnaire	End of dosing day	Association with W12 alcohol outcomes, adjusted for baseline
6.	Safety			
•	Adverse events	AE reporting	Throughout study	Descriptive

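### The two sensitivity analyses labelled as conservative MNAR scenarios do not bound the treatment effect: one gives every dropout in both arms half of baseline as a known value, the other is a complete-case analysis

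*SAP*

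**What the plan says.** Under Missing data, the SAP accepts that MAR may fail and announces sensitivity analyses by "setting missing observations to extreme but realistic values to bound realistic effect size". Under Sensitivity analysis it places them in an MNAR setting, where "missingness is assumed to potentially depend on factors related the unobserved Week 12 outcome values", and calls the scenarios conservative. Two are listed:

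- "Complete-case analysis: Analyses will be restricted to participants with observed values at both baseline and the Week 12 endpoint".
- A one-value imputation, labelled as the conservative scenario: when Week 12 is absent, "the continuous Week 12 outcome will be imputed as a 50% reduction" relative to that person's own starting level (0.5 × baseline), after which the primary model is refitted.

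The second rule makes no distinction by arm. No range of values and no tipping point is given. On the amount of missing data, the Sample size section reports that the "observed dropout rate was substantially lower than anticipated (13%), resulting in 59 enrolled participants, of whom 51 completed the primary endpoint assessment". The split by arm is not given. The Outcomes table schedules percentage of heavy drinking days (PHDD) at baseline and Weeks 4, 8 and 12.

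**The concern.** These are the only prespecified missing-data stress tests of the primary result. If dropout is informative, the case to examine is that dropouts in one arm did worse than the model predicts and those in the other did not. A single value shared by both arms does not examine it. A reader who sees a conservative MNAR scenario agree with the primary analysis may credit the result with a robustness that was never tested.

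Three further problems follow:

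- A deterministic single imputation treats guesses as observations, so the standard error is too small.
- The rule overrides what a dropout's own Week 4 and Week 8 records show.
- Complete case fills in no value and models no dependence on the unobserved outcome, so it does not address the mechanism that the SAP names.

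**Working it through.** **Inputs from the SAP.** 59 enrolled, 51 with the primary endpoint, 1:1 allocation, imputed value 0.5 × baseline in both arms. Missing = 59 - 51 = 8, and 8/59 = 13.6%, in line with the stated 13%.

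**Assumed, because the SAP does not give them.** Arms of 30 (psilocybin) and 29 (placebo), all 59 dosed, the split of the 8 by arm, and the completers' change. If some of the 59 were not dosed, fewer than 8 values are missing in the analysis set.

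**1. One point, and the midpoint.** Let c1 and c0 be the completers' Week 12 level as a fraction of baseline (psilocybin, placebo) and f1 and f0 the fractions missing. The difference under the rule is

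[(1 - f1)·c1 + 0.5·f1] - [(1 - f0)·c0 + 0.5·f0].

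The bounds put one arm's dropouts at baseline (1) and the other's at zero (0), then the reverse. Averaging the two bounds gives 0.5 in both arms, so the rule always returns their midpoint.

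Example, falls of 60% and 30%, 4/4 missing: (26×40 + 4×50)/30 - (25×70 + 4×50)/29 = 41.3 - 67.2 = -25.9.

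| Completers' fall (psilocybin/placebo) | Missing (psilocybin/placebo) | Completers' difference | Rule | Bounds |
|---|---|---|---|---|
| 60% / 30% | 4/4 | -30.0 | -25.9 | -12.3 to -39.5 |
| 40% / 20% | 4/4 | -20.0 | -17.2 | -3.6 to -30.8 |
| 40% / 20% | 8/0 | -20.0 | -22.7 | -9.3 to -36.0 |
| 75% / 55% | 8/0 | -20.0 | -13.3 | 0.0 to -26.7 |
| 75% / 55% | 0/8 | -20.0 | -21.4 | -7.6 to -35.2 |

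(All in % of baseline; negative favours psilocybin.)

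**2. Direction.** The rule changes the difference by f1·(0.5 - c1) - f0·(0.5 - c0). If psilocybin completers fall by more than 50% and placebo completers by less, both terms push toward zero. If psilocybin completers fall by less than 50% and dropout is mainly in that arm, the change favours psilocybin (row 3). If both arms fall by more than 50% and dropout is mainly on placebo, it can also favour psilocybin (row 5).

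**3. Arm-specific stress, in PHDD points.** Assume baseline 60 and falls of 65% and 40%, so completers are at 21 and 36 (difference -15.0).

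- 4/4 missing, rule: (26×21 + 4×30)/30 - (25×36 + 4×30)/29 = 22.2 - 35.2 = -13.0.
- 4/4, psilocybin dropouts at baseline, placebo dropouts like placebo completers: (26×21 + 4×60)/30 - 36 = 26.2 - 36 = -9.8.
- 4/4, the mirror: 21 - (25×36 + 4×60)/29 = 21 - 39.3 = -18.3.
- 8/0 missing: rule 23.4 - 36 = -12.6; psilocybin dropouts at baseline 31.4 - 36 = -4.6.

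**4. Standard error.** Simulated baseline-adjusted ANCOVA: 2,000 runs, residual SD 25 points, baseline PHDD uniform from 5/28 to 100%, values missing at random within arm. Each t is mean estimate over mean SE.

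| Falls, missing | All 59 observed: SE | Complete case: SE, t | Rule: SE, t |
|---|---|---|---|
| 60/30, 4/4 | 5.80 | 6.26, -2.53 | 5.46, -2.50 |
| 40/20, 8/0 | 5.95 | 6.47, -1.65 | 5.58, -2.26 |
| 40/20, 0/8 | 5.94 | 6.49, -1.65 | 5.73, -1.00 |

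In the first row the SE falls by 1 - 5.46/6.26 = 13%, to below what it would be with all 59 values observed. The estimate shrinks (-15.8 to -13.6 points) while t hardly moves. In the second row t goes from just short of the one-sided 0.05 threshold (about 1.67) to well past it. A second set of assumptions (residual SD 24, baseline SD 22, slope 0.5) gives 6.74 and 5.86, again 13%.

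**5. Complete case.** It is valid if missingness is unrelated to the Week 12 value given baseline and arm. The mixed model also allows missingness to depend on observed Week 4 and Week 8 values, so for PHDD complete case assumes more than MAR.

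**6. Scope.** If the rule covers every continuous outcome, a participant with 70% drinking days and 30% abstinent days becomes 35% and 15%. These sum to 50 rather than 100, and the same person improves on one measure and worsens on the other.

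**The case against.** A reader might infer that the rule favours psilocybin, or never counts against it. The SAP does not support that. With equal dropout and a real benefit, a common value pulls the estimate toward zero by roughly the missing fraction (-30.0 to -25.9). With all dropout on placebo it can weaken the result clearly (t from -1.65 to -1.00). What stands is that no arm-specific stress is imposed and the direction is not guaranteed.

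The 13% loss of standard error is measured against complete case, whereas the planned primary model is a repeated-measures mixed model. If dropouts were seen at Weeks 4 and 8 and the within-person residual correlation is 0.6 to 0.8, that model's SE is about 6.5 to 6.6 against 5.9 under the rule, a gap of about 10%. It is near 13% if dropouts have no post-baseline data. The direction holds; the size depends on assumptions.

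The 8/0 split is extreme. If dropout is unrelated to arm, all 8 falling in the arm of 30 has probability of about 0.3%. It shows what the rule can do, not what is likely.

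It is also tempting to say that the rule will be applied to % "abstinent days", AASE, MAAS and SF-36, where higher is better, or that it will halve MCV. The bullet speaks of one continuous outcome and of refitting the primary model, which can mean PHDD only. The neuroimaging remark in the complete-case bullet points to a wider scope. The text does not settle it, so the fair criticism is that the scope is not stated.

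Finally, complete case is a common supplementary analysis, and for outcomes measured only at baseline and Week 12 its assumption essentially coincides with MAR. The fault is the MNAR label, not its presence.

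**Conclusion.** The concern holds in a limited form. Neither listed analysis delivers the bounds that the SAP promises. The half-baseline rule gives the midpoint of the range from zero to baseline. In the illustrations that range is about 27 percentage points of baseline wide, and the rule reveals none of that width. Conservative is a property the rule has for some data and not for others. Its standard error is too small, by about 13% against complete case under the assumed ANCOVA and probably less against the planned mixed model. Complete case is mislabelled, and the rule's scope is unclear.

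The sizes rest on assumed completer changes and residual SD, up to 8 missing, and an unknown split by arm. It should not be inferred that the primary result is invalid or biased toward psilocybin: the primary estimate and test are untouched, few values are affected, and the SAP openly says that MAR may fail. This should be fixed, but it does not undermine the primary analysis.

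**What to change.** For PHDD, replace the half-baseline rule with delta-adjusted multiple imputation. Shift one group's missing Week 12 values stepwise from their MAR prediction to the participant's own baseline while the other group stays at MAR, then run the mirror. Write it symmetrically for group 1 and group 2, so that it runs under the blinded labels in the Blinding section and the scenarios are named after unblinding. Report both ends and any tipping point. In the 4/4 illustration in PHDD points, this would show about -9.8 to -18.3 (taking completer means as the MAR values) where the rule shows only -13.0.

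State that the halving rule is not applied to other outcomes. Keep the complete-case analysis but list it as supplementary, not as MNAR.

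The cost is SAP wording and a short script for at most 8 participants, with no new data. It is best done before lock and unblinding, otherwise as a dated amendment.
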